1. TITLE

Randomized controlled trial, double blind, phase III, to evaluate the immunogenicity of an adjuvanted influenza vaccine among health care personnel (EDUCATE)

2. STUDY SUMMARY

Health care personnel (HCP) frequently receive annual influenza vaccinations and a substantive proportion of them might have attenuated or no response to additional standard dose influenza vaccines. In this population that is seasonally exposed to influenza illnesses and repeatedly vaccinated using standard dose (SD) vaccines, adjuvanted (AD) vaccines might elicit a better immunity than the typically used SD. We therefore propose to conduct a double-blinded randomized controlled vaccine trial among HCPs to determine if AD influenza vaccines generate superior seroprotection against influenza than SD vaccines particularly among previous sub-optimal responders.

The trial will be conducted at two hospital sites in Lima-Peru during the 2022 influenza season. It has annual circulation int the country, but with increases during the months of June to October, which coincides with winter. The study is aimed to HCP who were enrolled in the Cohort study of Influenza and other Respiratory Viruses among HCP in Peru (approximately 1500). The number of participants to be enrolled is 800 approximately. The study design is a randomized, double-blind vaccine trial. Eligible HCP at each site who consent to participate will be randomized 1:1 to receive either a single dose of AD (FLUAD, quadrivalent, Seqirus) or SD (VaxigripTetra, quadrivalent, Sanofi-Pasteur). Participants, researchers and laboratory staff performing the assays will be blinded to the vaccine information.

Participants will be invited to attend the study site for a study screening and assessment of eligibility criteria, if they agree to participate and once consent form is signed, they will visit the site at day 0 for vaccination and medical assessment. Another brief medical adverse event assessment will be performed on days 3 and 7. Participants will be also prompted to begin active surveillance for acute illnesses as soon as US Center of Prevention and Control of Disease (US CDC) and the study site PI confirm that seasonal influenza is circulating locally or there are indicators that circulation is imminent. During the influenza season, participants will be followed up twice a week via SMS or phone calls to assess if they become sick with a respiratory event, if so, they will be asked questions about their illness through an acute illness survey and a swab sample will be requested.

Participants will also be notified when local influenza circulation or the season has ended via SMS message, an email, or a telephone call, based on the same epidemiological data used to trigger the start of the season. A survey will be filled on day 28 post vaccination as well as at the end of the influenza season.

All participants will have blood collected just prior to vaccination (Day 0), 28 days post-vaccination (Day 28), and at the end of the influenza season, to evaluate immune responses to vaccination. We will evaluate differences of seroconversion and seroprotection between AD and SD vaccination groups. In addition, we will use multivariable modelling to assess risk factors for poor immunogenicity and to assess effect of repeated vaccination.

As an optional sub-study, we will examine indicators of cell-mediated immune (CMI) response to influenza vaccination. This part of the study, which is optional to participants, will require collection of additional blood samples at pre-vaccination and days 7 and 28 post-vaccination.

See study timeline which includes the schedules of evaluation per participant.

3. STUDY TIMELINE

STUDY TIMELINE_SCHEDULE OF EVALUATIONS							
Visit Number	1	2	3	4	5	6	
Day of Study	Screening	D0	D3	D7	D28	D180-200	
Activities							
Informed Consent	x						
Medical History Review		x					
Vital Signs		х	х	х			
Complete Physical Examination		x	x	x			
Targeted Physical Examination		x	x	x			
Pregnancy Prevention Counseling	Х*						
Pregnancy Test	x						
Eligibility Confirmation	Х						
Enrollment CRF		х					
Randomization		х					
Compensation		х	х	х	х	х	
Vaccination /Product Administration (filling form)		x					
Injection Site Evaluation		х	х	х			
Adverse Event Evaluation		х	х	х			
Phone Contact (clinic visit if needed)/filling forms			x	x	x	x	
Respiratory surveillance twice a week during influenza season (acute illness detection, sample collection, storage, filling forms)							
Blood sample		х			х	x	
РВМС		х		х	х		
Storage of samples		х		x	х	x	
Packaging/Shipping						х	

*in case a reevaluation is required, it will be scheduled in 1 to 4 weeks

5. LOCATION

The study will be performed at two tertiary hospitals in Lima, Peru: Cayetano Heredia National Hospital, and Arzobispo Loayza National Hospital. The two hospitals were selected because have previously participated of an influenza vaccine effectiveness cohort study among healthcare personnel (HCP) and contributed 1,500 participants.

5.1 QUALITY TRAINING

CDC, Influenza Division, NAMRU6 and the National Hospitals Cayetano Heredia, and Arzobispo Loayza have collaborated in influenza research during the past six years. Currently, these institutions are conducting a cohort study in the two hospitals to evaluate influenza vaccine effectiveness among HCP. Each hospital site has at least a Principal Investigator, one physician for enrolment, one nurse for administration of vaccines and 3 nurses for screening and follow-up.

6. HYPOTHESIS

Adjuvanted (AD) influenza vaccine is more immunogenic among HCP, as compared to the non-adjuvanted Standard-Dose (SD) influenza vaccine.

7. OBJECTIVE

Primary objective:

-To determine if AD influenza vaccine generates superior immunogenicity than the non-adjuvanted SD influenza vaccine, at approximately 28 days after vaccination and at the end of season, among HCP

Secondary objectives:

-To compare immune responses post-vaccination, at approximately 28 days after vaccination and at the end of season, among HCP with a history of PCR-confirmed influenza infection during any of the six cohort years (2016 to 2021)

-To compare immune responses post-vaccination, at approximately 28 days after vaccination and at the end of season, among HCP with no history of PCR-confirmed influenza infection during the six cohort years (2016 to 2021), among those with data available for the six cohort years -To examine whether the number of prior influenza vaccination during the preceding 10 years, as documented by medical records, modifies immune responses after receipt of vaccination with AD or SD influenza vaccine, at approximately 28 days after vaccination and at the end of season -To evaluate laboratory-confirmed influenza illness rates in the group receiving AD influenza vaccination compared to the group receiving SD influenza vaccination

-To analyze and identify risk factors for sub-optimal response (lack of seroconversion/seroprotection) to SD and/or AD influenza vaccines

- To assess the adverse events among HCP receiving SD and AD influenza vaccines

the studies in reference are those entitled: "Effectiveness of influenza vaccine to prevent infection by influenza virus, loss of hours of work and patient exposure: A prospective cohort study in health workers " that was carried out during the years 2016 to 2019 and "Effectiveness of the influenza vaccine to prevent infection by the influenza virus, loss of working hours and patient exposure: A prospective cohort study in health workers in the context of the COVID-19 pandemic "that was carried out between 2020-2021. Both studies were observational epidemiological studies in hospitals in Lima .

8. JUSTIFICATION

An adjuvanted quadrivalent inactivated influenza vaccine (aQIV), FLUAD[®] Quad (Seqirus) has been licensed in 38 countries including the USA since 2015 for use in persons aged 65 years and older [1, 2].

FLUAD[®] Quad is a standard-dose influenza vaccine that contains an adjuvant named MF59. This adjuvant is naturally found in humans and enhances immune response to vaccination [1, 3].

Studies have shown a significantly improved immunogenicity and seroprotection among adults aged \geq 65 years who received an AD influenza vaccine when compared to those vaccinated with a non-adjuvanted SD [4, 5]. A randomized study by Cowling et al (2019) [4] showed that MF-59 vaccine, among other enhanced vaccines, presented significantly higher proportion of participants who achieved a 4-fold or greater rise in postvaccination titers from day 0 to Day 30, with a postvaccination titer \geq 40, a significantly higher geometric mean titer at Day 30, compared to those who received a standard dose vaccine. In addition, they observed a trend rise of vaccine-specific T-cells at 7 and 30 days postvaccination with MF59. Studies have also shown effectiveness of adjuvanted influenza vaccine against influenza-associated outcomes [6].

Studies not noted safety concerns, and while AD vaccine has been associated with increased reactogenicity compared with non-adjuvanted SD vaccine in some studies, these symptoms have generally been reported to be mild or moderate and self-limited [1, 3, 4, 7, 8].

Not all people who receive SD influenza vaccines develop a protective antibody response to influenza virus infections. Vaccinee characteristics can be associated with poor immunogenic response to influenza vaccination [9-17].

In the Americas, health authorities recommend that HCP receive annual influenza vaccination [18] to protect them from influenza illness, its potentially serious complications, and associated absenteeism, as well as to limit contagion from providers to their frequently vulnerable patient population. As such, HCPs frequently receive annual vaccinations and a substantive proportion of them might have attenuated or no response to additional standard dose influenza vaccines. In this population that is seasonally exposed to influenza illnesses and repeatedly vaccinated using SD vaccines [19, 20], AD vaccines might elicit a better immunity than the typically used SD. We therefore propose to conduct a double-blinded randomized controlled vaccine trial among HCPs to determine if AD influenza vaccines generate superior seroprotection against influenza than SD vaccines particularly among previous sub-optimal responders.

9. ANTICIPATED POLICY IMPACT

If our hypothesis is correct, health authorities might want to evaluate the marginal benefit of vaccinating HCP with AD rather than non-adjuvanted SD influenza vaccines to improve their seroprotection and the interruption of transmission to other contacts.

10.STUDY DESIGN

This study is designed as a randomized controlled trial (RCT), double blind, phase III, to evaluate the superior immunogenicity of an adjuvanted influenza vaccine in comparison with the immunogenicity of a non-adjuvanted standard dose influenza vaccine , among health care personnel

10.1 Study population

Eligible adult participants (age 18 or older) will work in one of the selected healthcare facilities (Cayetano Heredia National Hospital, and Arzobispo Loayza National Hospital) and will meet the following inclusion criteria:

Inclusion criteria:

- Be aged ≥18 years old;
- Have participated in the healthcare personnel cohort study between 2016 and 2021.
- Work at the facility full-time (≥30 hours per week);
- Have routine, direct, hands-on or face-to-face contact with patients (within 1 meter) as part of a typical work shift, including, but not limited to, physicians, nurses, respiratory therapists, physical therapists, unit clerks, radiograph technicians, medical assistants, and transporters;

- Work at the facility for ≥1 year prior to enrollment and planning to continue working at the facility for one year after enrollment;

- Willing to receive influenza vaccination (either AD/SD)

-Women of childebaring age have to complete the following criteria:

- Negative urine pregnancy test performed by the study staff within 24 hours preceding receipt of vaccination
- Willing to use use another reliable form of contraception approved by the Investigator that they select to use for at least 2 months after receiving the vaccine. If they are not using, we will provide access to contraceptives.
- Do not be in breastfeeding period

Exclusion criteria:

- Be vaccinated against influenza in the current season (influenza season 2022)
- Have severe, life-threatening allergies against influenza vaccines, eggs or influenza vaccine components
- Have a history of Guillain-Barré Syndrome or other autoimmune diseases
- Received blood or blood products within 3 months before enrollment
- Be pregnant, confirmed by rapid pregnancy test

The participation from each subject will be from the enrollment (March approximately) until the end of the influenza season

10.2 Sample size

We calculate that we will need a minimum sample size of 118 participants per vaccination group for detecting a difference between two proportions (based on seroprotection percentages for influenza A(H1N1p) of a previous study:91% vs 78% [21]) (see below), considering a 95% confidence level (two-sided) and 80% statistical power. To account for loss to follow up, we will increase sample size by 20%, so sample size will be a minimum of 142 subjects per group (Table 1).

Table 1. Sample size calculation based on published seroprotection rates for different influenza viruses

Seroprotection	P1 (AD group)	P2 (SD group)	n/per group	With additional 20%
subtypes				
Influenza A(H1N1p)	91%	78%	118	142
Influenza A(H3N2)	No information	No information		

Influenza B	No information	No information		
Where P1=percentage o	f seroprotection for AD g	roup and P2=percentage	e of seroprotection for S	D group

However, although the sample size calculation yields 142 participants per group, there may be different scenarios in which the difference between groups is shortened. In the following table, differences of 10-20% are estimated (Table 2). As a result of this calculation, it is estimated that a sample size of approximately 400 individuals per group will allow us to detect a difference of at least 10% considering a 78% seroprotection rate in the group vaccinated with non-adjuvant vaccine.

Table 2. Different scenarios in seroprotection rates (28 days post-vaccination) per group and sample size calculation

Seroprotection rate in SD group	Relative increase (5) in AD group vs SD group	n per group	Total n	With additional 20%
78%	10%	359	718	862
78%	20%	70	140	168
88g%	10%	131	262	314
88%	15%	58	116	140

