 start of the contraceptive method.
- All screening subjects will be assigned a screening subject identification number and listed in a screening log. Those subjects remaining eligible after the physical exam and evaluation of screening will be enrolled and be given a subject enrollment number prior to be immunized.

Study staff will provide participants with a copy of the informed consent as well as an informative brochure including information of the study, investigational product, and contact information of study staff and schedule of activities (Appendix D). We anticipate to recruit up to a maximum of 800 participants in the study, 400 per group. The informed consent will include permission to access medical records and link data from the previous study with data from the current study.

Subjects who fail screening may be re-screened if the Investigator thinks it is likely the subject will fulfill the inclusion/exclusion criteria requirements at a later time.

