10.13 Study outcomes

The primary outcome to be measured will be seroconversion at day 28 after vaccination. Seroconversion will be defined as having a haemagglutination inhibition (HI) geometric mean titre (GMT) of \geq 1:40 in the case the pre-vaccination HI GMT <1:10 or having a four-fold rise in titre in the case the pre-vaccination HI GMT \geq 1:10. We will also measure HI GMT at the end of season. Seroprotection will be defined as having an HI GMT \geq 1:40.

Other outcomes that will be measured include:

-reactogenicity to vaccination

-acceptability of AD influenza vaccination

-acute respiratory illness (ARI)

-ARI-associated outcomes (absenteeism, medical visits, hospitalization, other)

-laboratory-confirmed influenza and other respiratory pathogens

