Laboratory- confirmed influenza illness rates in HCP receiving AD	Clinical	Comparison of persons who did and did not become sick with influenza after receiving the AD or SD	Person became sick with influenza after receiving AD or SD vaccine Person did not become	Nasal swab specimen tests positive for influenza by PCR	Quantitative Discrete	PCR assay (laboratory)
vaccine		vaccine	sick with influenza after receiving AD or SD vaccine	Nasal swab specimen tests negative for influenza by PCR		

Secondary Objective 6: To assess the adverse events among HCP receiving SD and AD influenza vaccines

				Criterios de	Tipo de	Instrumento de
Variable	Dimensión	Indicador	Valores	medición	variable/indicador	medición
	(Dimension)	(Indicator)	(Values)	(Measurement criteria)	(Type of variable/indicator)	(Measurement instrument)
Adverse events in HCP receiving AD vs. SD vaccine	Anticipated (Clinical)	Local reactions: pain on vaccination site, swelling, lump itching, bruising	Yes	Person had a local and/or systemic reaction(s) after receiving AD or SD vaccine	Quantitative Discrete	Post-vaccination surveillance via follow-up visits and monitoring (calls, surveys)

	AND/OR Systemic reactions: fever (≥38°C), muscle ache, joint pain, headache, malaise, fatigue, weakness, sweating, shivering	No	Person did not have a local and/or systemic reaction(s) after receiving AD or SD vaccine		
	Death, life- threatening adverse event, hospitalization or prolongation of existing	Yes	Person had a serious adverse event after receiving the AD or SD vaccine		Post-vaccination surveillance via
Serious, Unanticipated (Clinical)	hospitalization, a persistent or significant incapacity affecting normal life activities, and other unanticipated event that seriously impacts the health of participants	No	Person did not have a serious adverse event after receiving the AD or SD vaccine	Quantitative Discrete	follow-up visits, monitoring (calls, surveys), and hospitalizations

Below we describe the statistical tests that we will perform to address each primary and secondary objective, highlighting which study population will be included for each analysis. All statistical tests will be performed with a significance level of 5% and a statistical power of 80%.

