Primary objective: To determine if AD influenza vaccine generates superior immunogenicity than the nonadjuvanted SD influenza vaccine, at approximately 28 days after vaccination and at the end of season, among HCP. We will use Wilcoxon signed-rank tests to assess HI GMT differences and differences in proportions of HCP who seroconverted and were seroprotected between AD and SD vaccination groups. All HCP included in the clinical trial will be included as the study population for these analyses.

Secondary objectives:

1) To compare immune responses post-vaccination, at approximately 28 days after vaccination and at the end of season, among HCP with a history of PCR-confirmed influenza infection during any of the six cohort years (2016 to 2021). The outcome variables will be the same as those of the primary objective matrix of variables, but dividing the enrolled study population to include only the HCP with a history of PCR-confirmed influenza infection during any of the six-year cohort (2016-2021). We will use Wilcoxon signed-rank tests to assess HI GMT differences and differences in proportions of HCP who seroconverted and were seroprotected between AD and SD vaccination groups. Only HCP in the clinical trial with a history of PCR-confirmed influenza infection during any of the six cohort years (2016 to 2021) will be included as the study population for these analyses.

2) To compare immune responses post-vaccination, at approximately 28 days after vaccination and at the end of season, among HCP with no history of PCR-confirmed influenza infection during the six cohort years (2016 to 2021), among those with data available for the six cohort years. The outcome variables will be the same as those of the matrix of variables in the primary objective, but dividing the enrolled study population to include only the HCP with no history of PCR-confirmed influenza infection during any of the six-year cohort (2016-2021). We will use Wilcoxon signed-rank tests to assess HI GMT differences and differences in proportions of HCP who seroconverted and were seroprotected between AD and SD vaccination groups. Only HCP in the clinical trial with no history of PCR-confirmed influenza infection during any of the six cohort years (2016 to 2021) will be included as the study population for these analyses.

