5) To evaluate laboratory-confirmed influenza illness rates in the group receiving AD influenza vaccination compared to the group receiving SD influenza vaccination. Using data collected through active surveillance, we will calculate incidence densities and use descriptive statistics and Z-test to assess differences in the proportion of HCPs who had laboratory-confirmed influenza (as determined by PCR on nasal swab samples) during the period of the clinical trial among the HCP who received the influenza vaccines AD vs. SD. A Cox regression model will be used to adjust the risk of developing influenza between both groups according to demographic and occupational characteristics. Health personnel participating in the clinical trial will be included as a study population for these analyzes.

6) To assess the adverse events among HCP receiving SD and AD influenza vaccines. Using data collected through active surveillance, we will use descriptive statistics and the Z test to assess the differences in the proportions of adverse events (anticipated and serious) between the HCP who received the AD and SD

influenza vaccines. All health personnel participating in the clinical trial will be included as a study population for these analyzes.

Table 1: Summary of Analysis by Endpoints and Analysis Populations.

OBJECTIVE	VALUATION CRITERIA	STATISTICAL TEST	POPULATION OF ANALYSIS
Primary Efficacy Analysis			
To determine if the AD influenza vaccine generates superior immunogenicity than the vaccine against SD influence without adjuvant among the HCP.	Immunogenicity - superior serumconversion of AD vaccine versus SD vaccine in HCP.	Wilcoxon signed rank test.	PP population
Secondary Efficacy Analysis			
To compare the post-vaccine immune response, in approximately 28 days after vaccination and at the end of the influenza season, among the HCP with a history of influenza infection confirmed by PCR result during any of the 6 years during the previous cohort study (2016 to 2021).	Post-vaccination immune responses, approximately 28 days after vaccination and at the end of the season, among HCPs with a history of PCR-confirmed influenza infection	Wilcoxon signed rank test.	ITTm1

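### The named primary outcome is day-28 seroconversion, but section 10.2 sizes the trial only on seroprotection, so the 80% power is not established for the primary outcome; and the row behind 400 per group does not fit the 800 maximum after the plan's own loss allowance

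*Combined protocol and SAP*

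**What the plan says.** Section 10.13 states: "The primary outcome to be measured will be seroconversion at day 28 after vaccination". The summary table in 11.1 agrees; its criterion for the primary efficacy analysis reads "Immunogenicity - superior serumconversion of AD vaccine versus SD vaccine in HCP".

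Section 10.2 works on another endpoint. Its opening calculation is "based on seroprotection percentages for influenza A(H1N1p) of a previous study:91% vs 78" per cent, giving 118 per group, or 142 with 20% added. Table 2 in that section lists four further scenarios, all of them seroprotection rates at 28 days. The enrolment target comes from that table: "a sample size of approximately 400 individuals per group will allow us to detect a difference of at least 10" per cent, taking 78% seroprotection in the standard-dose group. The matching row shows 359 per group, 718 in total and 862 with the 20% allowance, and its effect column is headed as a relative increase. Section 10.4 says: "We anticipate to recruit up to a maximum of 800 participants in the study, 400 per group".

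Section 11.1 says of the whole analysis: "All statistical tests will be performed with a significance level of 5% and a statistical power of 80" per cent. Under the primary objective it lists HI titres and "differences in proportions of HCP who seroconverted and were seroprotected between AD and SD vaccination groups", so seroprotection is one of the measures analysed there.

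**The concern.** The two endpoints in 10.13 are different proportions. Seroprotection needs only a post-vaccination titre of at least 1:40. Seroconversion depends on the starting titre: at least 1:40 from below 1:10, and otherwise a four-fold rise. Someone at 1:40 both before and after vaccination is seroprotected but has not seroconverted. Sections 2 and 8 describe this population as repeatedly vaccinated, with a substantial share who may respond weakly or not at all. A seroprotection rate of 78% therefore cannot stand in for a seroconversion rate.

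At stake is how the primary result is read. If the seroconversion comparison is null, the plan offers no difference that the trial was sized to detect. The second issue is whether 80% power is delivered even for seroprotection, in the scenario that 10.2 uses to justify 400 per group.

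**Working it through.** **Inputs.** From 10.2: two-sided 5% level, 80% power, seroprotection 78% (standard dose) and 91% (adjuvanted), Table 2 scenarios, and a 20% allowance applied by multiplying by 1.2. From section 2: 1:1 allocation. From 10.4: at most 800, 400 per group. Seroconversion rates: none in the documents, so they are assumed below.

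**1. Reproducing the plan.** The unpooled normal approximation is n = (1.960 + 0.842)² × [p1(1−p1) + p2(1−p2)] / (p1−p2)², with (1.960 + 0.842)² ≈ 7.849.

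| Scenario | Calculation | Result | Plan |
|---|---|---|---|
| 78% vs 91% | 7.849 × (0.1716 + 0.0819) / 0.0169 | 117.7 | 118 |
| 78% vs 86% | 7.849 × (0.1716 + 0.1204) / 0.0064 | 358.1 | 359 |
| 78% vs 94% | 7.849 × (0.1716 + 0.0564) / 0.0256 | 69.9 | 70 |

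The arithmetic for seroprotection is sound. The 10% row is 78% × 1.10 = 85.8%, rounded to 86%: a relative increase of about 8 points.

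**2. Fit with the maximum.** 359 × 2 × 1.2 = 861.6, so 862, which is above 800. With 400 enrolled per group, 359 evaluable leaves room for (400 − 359)/400 ≈ 10% loss, not 20%.

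**3. Seroprotection power at 800, 78% vs 86%.** With pooled variance under the null, power = Φ{[d√n − 1.960√(2p̄(1−p̄))] / √[p1(1−p1) + p2(1−p2)]}. Here d = 0.08, p̄ = 0.82, √(2 × 0.82 × 0.18) = 0.5433 and √0.2920 = 0.5404.

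| Evaluable per group | Basis | Power |
|---|---|---|
| 400 | no loss | Φ[(1.600 − 1.065)/0.5404] = 84% |
| 333 | 400/1.2 | Φ[(1.460 − 1.065)/0.5404] = 77% |
| 320 | 400 × 0.8 | Φ[(1.431 − 1.065)/0.5404] = 75% |

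**4. Seroconversion.** The same power formula, solved for the difference that gives 80% power, over assumed standard-dose rates:

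| Assumed standard-dose rate | Detectable difference, 400 evaluable | Detectable difference, 320 evaluable | Power for 13 points, 400 | Power for 13 points, 320 |
|---|---|---|---|---|
| 20% | 8.5 points | 9.5 points | 98.7% | 96.3% |
| 30% | 9.4 | 10.6 | 97.0% | 92.9% |
| 40% | 9.8 | 11.0 | 95.9% | 91.1% |
| 50% | 9.8 | 11.0 | 96.1% | 91.4% |
| 60% | 9.5 | 10.5 | 97.5% | 93.8% |

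The 13 points are the gap in the plan's opening calculation (91 − 78), used here only as a yardstick. All figures assume a between-group test of two proportions, as 10.2 does.

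**The case against.** The strongest reply is that 10.2 does size the primary objective. The variable table and the text in 11.1 list seroprotection alongside seroconversion under that objective, and sections 2 and 8 state the aim in terms of superior seroprotection. This stands, and it limits the point: the sizing is relevant to the objective, but not to the one outcome that 10.13 and the summary table single out.

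A second reply is that 800 is ample. The opening calculation needs only 2 × 142 = 284, and for 91% vs 78% power exceeds 99% even with 320 evaluable per group. That is right for a 13-point seroprotection gap. The shortfall in step 3 concerns the smaller effect on which 10.2 rests its figure of 400. It is modest, and since the plan gives its totals as approximate it is a matter of restating rather than redesign.

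Third, a confidence interval would still show which differences a null result excludes. That is true, but it does not supply the missing planning assumption.

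Three stronger readings are tempting, and the documents support none of them:
- A reader might infer that the trial is underpowered for seroconversion. With no rate or target given, that cannot be shown, and step 4 shows reasonable sensitivity over a wide range of rates.
- A reader might carry Table 2's 10% relative increase over to seroconversion and obtain very low power. No section proposes so small a seroconversion target.
- A reader might treat the 10% as open between relative and absolute. The column header says relative, and 359 is reproduced by 86%; a ten-point gap would give 7.849 × (0.1716 + 0.1056)/0.01 = 217.6. Only the wording of the sentence is loose.

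**Conclusion.** The point holds in two parts. First, the 80% power claimed in 10.2 and 11.1 is not established for the named primary outcome, because the plan contains no seroconversion rate or target difference. Over assumed standard-dose rates of 20–60%, the trial could detect 8.5–9.8 points with full data and 9.5–11.0 after 20% loss. Whether that is adequate depends on an expectation that the plan does not state. Second, for seroprotection, the scenario that justifies 400 per group is not delivered at 80% within the 800 maximum once the plan's own allowance is applied: power is 75–77%, against 84% with no loss.

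The second part rests on the plan's own rates. The first follows from comparing the sections; only its illustrative figures depend on assumed rates. The point should be corrected before analysis, but it does not call the enrolment target into question.

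**What to change.** Keep the maximum of 800.

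1. Make 10.2, 10.13 and the summary table in 11.1 name the same primary endpoint.
2. If it is seroconversion, state in 10.2 the expected day-28 rate in the standard-dose group, its source and the strain or strains it refers to. Give the difference detectable with 80% power at 400 evaluable per group and after 20% loss. If no rate can be justified, give this over a stated range, as in step 4.
3. If it is seroprotection, change 10.13 and the summary table, and restate the power for 78% vs 86% as 84% without loss and 75–77% after the 20% allowance.
4. In either case, reword the 10% in the text of 10.2 as a relative increase of about 8 points, and replace the blanket 80% power statement in 11.1 with the power for the primary comparison.

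The cost is text and one recalculated table, with no extra participants and no change to conduct. The sponsor has to find or justify a seroconversion rate, and must accept that the stated power may be somewhat less favourable after loss. Which test 11.1 names for the primary comparison is a separate matter.
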